12.0 Statistical Considerations

Counting for the attrition rate of 20% of most of the interventions with frail older adults, we expect to use data of 96 participants with 16 participants in each subgroup (Group 1A and B; Group 2A and B; Group 3A and B) for data analysis. To determine the effect of training using Exergaming, pre-post changes of balance, cognitive, gait and cardiovascular measures will be examined by ANCOVA. Results of the study from a sample size of 96 will enable us to conduct power analysis to plan for a larger scale RCT.

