5.0 Subject Enrollment

A total of 120 participants will be enrolled in the pilot study (see Research Design and Procedures for details).

We will initially recruit the participants by posting flyers (approved by the Institutional Review Board) at Geriatric and internal medicine by contacting [name], giving presentations to potential participants at various exercise centers and senior homes. We will also use social media, such as Facebook, Twitter, etc. to post flyer for recruitment. As a part of recruitment procedure, we will not be accessing the EMRs, and will get referrals from different physicians for those who are potentially eligible to participate in our study. Our research staff team will travel to various locations to provide the background education about our study and explain the procedures through the study involved and will show them the consent form. The consent form will provide enough information about the study and the interested people will be asked to provide their contact information, which will be noted down on a sheet. Later, one of the researchers mentioned on the Appendix P will contact them for a telephone screening. Individuals making the initial contact looking at flyers will also undergo the same telephone screening question and will be asked where they heard/read about the study. The initial telephone screening would determine their general health condition, preliminary eligibility. They will be asked to choose a group that they prefer to participate which includes 3 options- 1) Group 1: In-person assessments and inperson training (where all the tests and training sessions will be conducted in the laboratory); 2) Group 2: In-person assessments and online training (where only the tests before and after training will be conducted in the laboratory and they

[figure not shown]

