6.0 Study Design and Procedures

- This study will be a randomized controlled design.
- During the telephone screening, all the participants will be asked to choose a group that
 they prefer to participate which includes 3 options: Group 1: In-person assessments
 and in-person training; Group 2-In-person assessments and online training and Group
 3- Online assessments and online training.

[figure not shown]

- Figure 1 above shows recruitment and distribution of participants into differenct groups based on the options given for assessment and training to the participants during telephone screening.
- After the participants are allocated to groups 1,2 and 3 depending on their choice, each
 participant from every group will be randomly assigned either Group A (CogXergaming)
 or Group B (Matter of balance) for training by flipping a coin.
- Al the participants will be undergo 1-on-1 testing and training.
- Study protocol will vary according to the groups that the participants choose to be in (Groups 1,2 or 3).
- For Group 1 (In-person assessments and in-person training): Group A (CoXergaming) will undergo a total of 8 weeks session with first week and last week comprising of assessment. 6-week training will be delivered using the Nintendo Wii-Fit gaming system and a pointer mouse. Participants will visit the laboratory 3 times a week for 6 weeks with each session lasting for 60 minutes (18 training sessions). During training session, participants will wear a gait belt and will be guarded by a research assistant for safety. On the other hand, if the Group 1 participant gets assigned to Group B (Matter of balance) then participants from Group B will undergo a total of 10 weeks session with first week and last week comprising of assessment. The participants will undergo an 8-week (one session a week for 2 hours/day, 8 sessions in total) structured intervention specifically designed to reduce the fear of falling and to increase the engagement in PA.

| Test | Pre- test | CogXergaming/TeleXercise Intervention (6 weeks) | | | | | | | | | | | Post-test | | | | | | | |
|---------|--------------|---|---|---|---|---|---|---|---|---|----|----|-----------|----|----|----|----|----|----|-----|
| Session | 1-4 | 1 | 2 | 3 | 4 | 5 | 6 | 7 | 8 | 9 | 10 | 11 | 12 | 13 | 14 | 15 | 16 | 17 | 18 | 1-3 |
| Week | 1 | 2 | | 3 | | 4 | | 5 | | 6 | | | 7 | | | 8 | | | | |

| Test | Pre-test | M | latte | Post-test | | | | | | |

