- 1. The clinical balance tests performed pre-and post-intervention would present with a mild risk of losing balance while performing the activities. Subject would be remotely monitored by the research personnel and also asked to place a sturdy chair in front of them while performing these assessments.
- 2. The walking tests (2-minute step in place test and the training may be led to some amount of fatigue.
- 3. During the cognitive assessment which tests memory, attention, comprehension etc., participants may experience some disappointment if they are unable to perform a certain task.
- 4. The answering falls and physical activity questionnaire may have some questions about personal health information and daily physical activity habits and the subjects may be some discomfort while answering those questions.
- 5. During assessment and training sessions of Group 2 and 3, we will ask the "helper buddy" to note what the participant may be feeling. Incase of events like shortness of breath, excessive sweating, fatigue or muscle crams- the session will be stopped and the participant will be discontinued from the study

[figure not shown]

Figure 2: Adverse event protocol

Privacy related risk

Further, as all the tests will be performed in a home-based setting via online interface wherein the researcher personnel would be performing the assessments and training remotely, therefore at any point in time there is a potential for breach of privacy and confidentiality.

Potential Benefits:

Study participants will receive bone health status, balance performance from their osteoporosis screening and other physical ability tests. Such information can allow them to take any necessary preventive measures. In addition, this cognitive-motor exergaming is expected to promote significant benefits on reducing fall-risk by improving function of both the balance control and cognitive functions. Further, it delivers training via a low cost off-the shelf virtual gaming console for providing

repetitive, engaging and meaningful, task-orientated training. It also examines if the training-induced effects cause plasticity in the cognitive and motor control areas and networks in the brain. If participants demonstrate no gains, the training offered will maintain their optimal physical functioning and not result in any deterioration.

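### The analysis is built on the 96 of 120 participants expected to remain, with no all-randomised set or missing-data method, while a fatigue-based discontinuation rule may cost the two arms outcomes unequally

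*Combined protocol and SAP*

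**What the plan says.** Section 5.0 sets the intake: "A total of 120 participants will be enrolled in the pilot study". Under section 6.0, participants choose a delivery Group (1, 2 or 3) and each is then assigned to Group A (CogXergaming) "or Group B (Matter of balance) for training by flipping a coin".

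Section 12.0 gives the analysis. It begins "Counting for the attrition rate of 20% of most of the interventions with frail older adults" and continues "we expect to use data of 96 participants with 16 participants in each subgroup", the subgroups being A and B within each delivery Group. The method is that "pre-post changes of balance, cognitive, gait and cardiovascular measures will be examined by ANCOVA". Covariates are not named. The results "will enable us to conduct power analysis to plan for a larger scale RCT".

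Section 9.0 adds only the software and a pointer to section 12.0. Section 11.0 monitors reasons for dropout but gives them no analytic use. Neither section defines an analysis set, follow-up after stopping training, or a treatment of missing post-tests.

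Section 7.0, under the risks of online assessment and training, covers assessment and training sessions of Groups 2 and 3. For breathlessness, "excessive sweating, fatigue or muscle crams- the session will be stopped and the participant will be discontinued from the study".

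**The concern.** Aim 1 compares the randomised arms on balance, muscular fitness, cardiovascular fitness and global cognition. If only those who remain are analysed, the comparison keeps the protection of randomisation only where loss is unrelated to outcome, given the covariates.

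The section 7.0 rule makes that doubtful. Fatigue, breathlessness and cramps are plausibly linked to the fitness and balance being measured, and the rule ends study participation, not just the session. Arm A also has more sessions, with more exertion, in which the rule can be triggered. Loss could therefore be related to outcome and unequal between arms.

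Two things are at stake: the A v B estimate itself, and the effect size carried into the power analysis for the larger trial. Aim 1 also treats compliance as part of feasibility, so those who cannot tolerate training are central to its question.

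**Working it through.** **1. The plan's own figures.** 120 × (1 − 0.20) = 96, and 96 / 6 = 16. Both reproduce. The expected loss is 120 − 96 = 24. In expectation this is 60 falling to 48 per arm and 20 falling to 16 per subgroup. Section 5.0 says enrolled rather than randomised; treating the 120 as randomised follows from section 6.0, where each participant is assigned an arm.

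**2. What happens when an online participant tires.**
- Section 7.0 (Groups 2 and 3, both arms): the session stops and the participant leaves the study.
- Section 6.2 (online arm A training): the participant sits down and checks vital signs. Leaving the study is not mentioned.
- Section 6.1 (online adverse events): the session ends, and a physician is advised if symptoms last more than a day. Leaving the study is not mentioned.
- Section 7.0 (in-person training): the session ends. Leaving the study is not mentioned.

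The first three cannot all be followed as written, and which one staff apply decides who has a post-test.

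**3. Exposure by arm (section 6.2).** Online A: 18 sessions × 1.5 h = 27 h, including aerobic, dance and strength content. B: 8 sessions × 2 h = 16 h, partly discussion and problem solving.

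**4. Bias formula.** Let p be the proportion lost in an arm, and D the mean change of completers minus that of dropouts, in SD units after covariate adjustment. The completer mean exceeds the full-arm mean by p × D, so

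bias(A − B) = pA × DA − pB × DB.

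This is zero if D = 0 in both arms, or if p and D are the same in both arms.

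**5. Illustration.** The documents give neither p by arm nor D. Assume a risk h per training session of 1% or 2%, the same in both arms; the same D of 0.5 or 0.8 SD in both arms; and equal delivery Groups. Then pA = 1 − (1 − h)^18 and pB = 1 − (1 − h)^8. The rule covers two of three Groups, so the pooled gap is multiplied by 2/3.

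| h | pA | pB | Gap (points) | Gap × 2/3 | Bias, D = 0.5 | Bias, D = 0.8 |
|---|---|---|---|---|---|---|
| 1% | 16.5% | 7.7% | 8.8 | 5.9 | 0.03 SD | 0.05 SD |
| 2% | 30.5% | 14.9% | 15.6 | 10.4 | 0.05 SD | 0.08 SD |

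Rule-driven loss overall is (16.5 + 7.7)/2 × 2/3 = 8.1% at 1%, and (30.5 + 14.9)/2 × 2/3 = 15.1% at 2%. Both fit within the planned 20%.

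For outcomes measured with instruments used only in Groups 1 and 2, the multiplier is 1/2, giving 0.02-0.04 SD (D = 0.5) or 0.04-0.06 SD (D = 0.8). For Group 3 alone the multiplier is 1, giving 0.04-0.08 or 0.07-0.12 SD.

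**6. Sensitivity to the exposure unit.** Suppose the whole 20% attrition, in all Groups, came from an equal risk per session (1.73%). Loss would be 27.0% in A and 13.0% in B. With equal risk per training hour (27 v 16 h) it would be 24.6% v 15.4%. The gap narrows but keeps its sign.

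**7. Scale.** With 48 v 48 and no gain from covariates, the standard error is √(2/48) = 0.204 SD.

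**The case against.** The strongest reply has four parts.

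*The 96 is a forecast.* Section 12.0 does not use the word completers and does not say that a post-test from someone who stopped training would be discarded. That is fair. But no other analysis set is named, and section 7.0 takes the participant out of the study, so under that rule no post-test would be expected.

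*The rule does not depend on arm.* A reader might infer that the protocol makes dropout differ between A and B. It does not: the wording is the same for both arms and leaves out Group 1. Unequal loss is an inference from 18 v 8 sessions and their content.

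*Bias is not shown.* A reader might also infer that the comparison is biased in favour of CogXergaming. The documents do not support that. Low baseline fitness may be handled by ANCOVA if baseline is a covariate, and less fit participants might improve more rather than less. On the rates above, the bias would reverse if DB exceeded about twice DA (16.5/7.7 = 2.1; 30.5/14.9 = 2.0). Sections 6.1 and 6.2 may also mean that few people are removed. The adverse event flow chart in section 7.0 could not be read and might settle which rule applies.

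*The effect is small for a pilot.* A bias of 0.03-0.08 SD is well below a standard error of about 0.20 SD. This limits the urgency. But the estimate feeds the design of the next trial, and a larger sample would not remove such a bias.

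**Conclusion.** The concern holds in a limited form. The plan bases its analysis on the participants expected to remain, with 24 of 120 expected losses and no all-randomised set, outcome follow-up or missing-data method. Section 7.0 contains a rule that, if followed, loses outcomes in Groups 2 and 3 for fitness-related reasons, and it conflicts with sections 6.1 and 6.2. Because exposure differs by arm, such loss may be unequal and could bias A v B.

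Size and direction cannot be obtained from the documents. The range of about 0.03-0.08 SD towards A in a pooled comparison rests wholly on the assumed 1-2% risk per session, equal Groups, and a 0.5-0.8 SD smaller change in dropouts of both arms. This should be corrected before analysis; it does not show that the trial's result will be wrong.

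**What to change.** 1. In section 12.0, state that all randomised participants are analysed in the arm assigned, and that 96 is only the expected number with a post-test.
2. Reconcile sections 6.1, 6.2 and 7.0 on what follows fatigue and similar symptoms. Which clinical rule applies is for the investigators. Whichever it is, separate stopping training from stopping outcome collection, and invite those who stop to the scheduled post-test where the investigator considers it safe.
3. Specify ANCOVA of post-score on arm and baseline score, with delivery Group added only among Groups that share an instrument. Table 1 in section 6.4 gives Group 3 different balance, gait and cardiovascular tests, so for these analyse Groups 1 and 2 together and Group 3 separately.
4. Handle remaining missing post-tests by multiple imputation within arm, using baseline score, delivery Group where pooled, and sessions attended. State its assumption that missing scores resemble observed ones with the same values of these variables. With a single post-test, a mixed model alone adds little.
5. Report dropout by arm and reason, and give the completer analysis as a sensitivity analysis.

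The cost is wording, some follow-up contact with those who stop, modest analysis work and perhaps slightly wider intervals.

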13.0 Regulatory Requirements

13.1 Informed Consent

Oral consent will be obtained over the telephone during the initial phone screen. Those who are eligible and elect to participate will be provided with a written informed consent document (approved by the University of Illinois at Chicago IRB). Consent will then be obtained by the research coordinators. All study participant documents will be available in English. The consent form will explain all procedures, risks, and benefits of the study. The study Participant will

communicate their intention to leave the study clearly too any study staff personnel, and their confidentiality will not be breached. Participants will receive a signed copy of the informed consent document. Informed consent form for each group will be separate so as to avoid any confusion for the participant. For Group 1 and 2, informed consent will be obtained in person in the laboratory. For Group 3 (online-assessments and online-training informed consent process will occur remotely (online) using REDCap. The PI holds an account through which participants will be provide their Informed consent via e-sign. This process will be explained via 'Zoom meeting' to walk them through every process.

13.2 Participant Confidentiality

Participants' confidentiality would be maintained as all the identifying information will be de-identified using an alpha-numeric code at the time of enrollment and the Participant specific unique code will be used for all the data collection purposes. All study records will be kept confidential by using a numerical code. A participant will not be identified personally in any report of the results. We will keep the identifying information at a centralized single location which will be locked, and it will be destroyed after the completion of the entire project. Only those who are active members of the research team will have access to the raw data. This research doesn't involve the use and disclosure of protected health information.

13.3 Unanticipated Problems

Any unanticipated problems will be reported to the IRB by submitting a "Prompt Report" form.

